**Clinicaltrials.gov identifier NCT02247336**

**Version 16**

**February 11, 2020**

## Protocol: The Impact of Family History and Decision Support on High-Risk Cancer Screening

**Introduction.** Risk assessment through family health history (FHH) permits tailoring of prevention strategies and treatment regimens to an individual's familial risk level. Although FHH is commonly accepted as an important risk factor for common, chronic diseases, it is rarely used in clinical practice as part of a structured risk assessment due to time constraints for the office visit, lack of standardization of FHH collection, failure to consolidate access into one location, and lack of confidence in identifying high-risk patients.

The Genomic Medicine Model (GMM) was developed by our university affiliate colleagues to address barriers to providers' use of structured risk assessment. The GMM comprises three components: 1) education of primary care providers (PCPs) and patients; 2) an IT-based platform, MeTree, that collects FHH from patients and generates a pedigree and decision support reports for patients and PCPs; and 3) provides support for patients and PCPs to interpret FHH information and adhere to recommendations. A standardized FHH assessment accompanied by decision support facilitates 3 important objectives: 1) identification of patients at higher risk, 2) genetic consultation referral for patients at risk for hereditary cancer syndromes, and 3) recommendation of guideline-based preventive care for patients of all risk levels.

Currently, the Veterans Health Administration (VA) has no system-wide, comprehensive, validated method for assessing FHH or providing decision support. The GMM offers a promising strategy for identifying patients at risk and providing risk-appropriate referrals and screening.

The goal of this study is to evaluate the feasibility and effectiveness of the GMM components (i.e., educational materials, FHH collection via MeTree, and decision support) in VA primary care practices to improve risk-appropriate CRC referrals and screening. This 3.5-year, mixed methods study involves a cluster randomized trial in which PCPs and their patients are randomized to immediate vs. delayed (wait-list control) patient-entered FHH data collection and decision support. The primary aims are:

**Aim 1:** Determine whether FHH collection via MeTree improves identification of patients at higher familial risk for CRC by comparing rates of high-risk identification in the medical record prior to study enrollment to rates of high-risk identification following MeTree completion.

**Aim 2:** Evaluate whether providing decision support to patients and PCPs improves risk-appropriate PCP referrals for, and patient uptake of, CRC screening/surveillance.

The secondary aims are:

**Aim 3:** Assess experience with decision support and effects on workflow from PCPs, and obtain information to inform eventual implementation in the VA healthcare system from administrative leaders, via qualitative interviews.

**Aim 4:** Conduct cost-consequence and budget-impact analyses of implementing FHH collection and GMM decision support in VA.

If MeTree effectively increases identification of high-risk Veterans, and decision support effectively increases appropriate CRC screening for high-risk Veterans, then we will be poised to inform and evaluate implementation of GMM in VA on a larger scale and for a larger disease set.

## Methods for Aims 1 and 2

**Sample selection and enrollment.** We will enroll primary care providers (PCPs) and patients from the Madison VAMC, Durham VAMC, Raleigh, Hillandale, and Greenville clinics. To achieve our target sample size of 500 patients who complete MeTree, we will enroll all eligible providers. We anticipate enrolling 40 providers, with 12-13 patients per provider; however, the number of patients enrolled per provider may vary if fewer providers enroll. PCP and patient eligibility will be determined from the following study inclusion/exclusion criteria.

Consented providers will be randomized to the immediate or delayed condition, in which a small subset of their patients will complete MeTree and receive decision support at enrollment or 12 months later. PCPs randomized to the immediate group will then receive additional with details of the study and educational materials throughout the study's recruitment period (those randomized to the delayed group will receive this information 12 months later). This additional detail includes information on the role of FHH in CRC and a description of the procedures to ensure that the decision support documents are available for the patient appointments. We will ask PCPs in this group not to discuss the decision support documents, process, or experience with other clinicians. We will minimize education provided to delayed wait list (control) providers by sending separate educational materials prior to initiating family history completion and decision support to wait-list control participants 12 months post-enrollment.

### Patient eligibility criteria will be determined by electronic data abstraction:

- Assigned to one of the enrolled PCPs
- At least one primary care appointment in the 18 months prior to enrollment
- Upcoming PCP appointment with assigned PCP
- Aged 40-64 years, confirmed via telephone screening

After providing verbal consent, participants will complete a telephone survey of self-reported screening (Appendix 1). One measure will be a self-report questionnaire that assesses the various recommended CRC screening test modalities, which was previously validated in the Veteran population by Drs. Fisher, [name], and [name]. For the other types of cancer screening, we will query receipt of breast magnetic resonance imaging, mammogram, , pelvic ultrasound, or genetic testing for screening purposes; these data will be examined in exploratory analyses. An advantage of collecting self-reported data is that we can capture receipt of any test received outside the VA. At this time, we will also administer a validated tool designed to assess computer proficiency, as this is a computer-based intervention. After completing the survey, participants will be informed of their randomization assignment, which is determined by whether their PCP was randomized to the immediate vs. delayed condition.

**Immediate Condition.** Participants in the immediate group will be provided with the choice of completing MeTree on their own online (at home, library, or wherever they can access it) or in person prior to their PCP visit. Participants in the delayed group will have this choice 12 months later. After receiving the signed HIPAA authorization form, or after completing the consent process when HIPAA is waived, study staff will log into the Duke software to register the patient user and will provide the patient with username and password, both of which will be identical, non-identifying, and generated by our tracking database. The username and password will be provided to the participant by mail, text message, or MyHealtheVet Secure Messaging, depending on veteran preference.

**Delayed (wait-list control) Condition.** We will inform control participants that we will contact them 12 months post-consent to complete MeTree. We will ask for contact information for a family member or friend to facilitate future contact. These participants will be informed that there is little risk associated with waiting, as CRC takes 7-10 years to develop. During the 12-month period, neither control patients nor their providers will receive further contact from study staff. Ten to 11 months following consent of the first participants, we will contact wait-list PCPs to provide the same

## Protocol: The Impact of Family History and Decision Support on High-Risk Cancer Screening

education that was provided to the immediate group. Also at 10 months following patient consent, we will mail a reminder letter to control patients informing them about the process to complete MeTree. At 11 months following baseline, we will telephone control participants to assess preference for mode of completion using the aforementioned procedures. If we are unable to reach control participants by telephone by 12 months following consent, we will mail another reminder letter. We will continue to try to reach control participants by telephone for up to 6 weeks following the 12-month time point. Note that control participants may not have an appointment scheduled at the 12-month time point. We will follow the same procedures as in the immediate arm with regard to uploading the PCP decision support document requiring PCP signature. PCPs may choose to order tests or schedule an appointment with control participants who are identified as high-risk. Likewise, patients who are informed that they are high-risk by the patient decision support document may call to request an appointment with their PCP following usual care procedures.

**Provider Departure.** If a patient's provider leaves before they are contacted by the study team, the participant's randomization will match that of their new provider, or the patient will be ineligible if the new provider does not consent to participate. Participants who have already completed MeTree prior to their provider leaving the VA will keep their assigned randomization per intent-to-treat principles.

**Procedures (both groups).** Consented participants will be provided with access to a worksheet to assist them in collecting FHH from their family members prior to logging onto MeTree. The worksheet is available for download from the MeTree website, but can also be mailed to the participants, depending on timing and preference. The worksheet queries names of children, parents, siblings, nieces/nephews, aunts/uncles, and grandparents; age now or at death of these individuals; diseases these individuals have had and age at diagnosis; and cause of death. A list of types of cancers, hereditary cancer syndromes, and other diseases is provided, along with definitions of various diseases and causes of death. Participants will be asked for their FHH for all of these diseases because MeTree has been designed to collect information on these diseases and decision support for additional diseases is ongoing. In this study, the primary outcome relates to CRC, with referrals and uptake of recommendations related to these other diseases as secondary outcomes.

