## Analyses for Aims 1-2

**Sample Size and Power Considerations.** The CRC screening rate of patients aged 50 years and older in VA is high, around 80%. However, this is based on the assumption that all patients are average-risk; as such, the risk-appropriate referral rate is not well-characterized. We estimate that the risk-appropriate CRC screening referral rate is 60% to 70%. Our final sample size calculation is based conservatively on the screening referral rate of 60%. Based on a type I error rate of 5% and Z test for the difference of two proportions adjusted for provider clustering, we will need approximately 480 patients (240 in each arm) to detect a 13% difference (i.e., 73% in the immediate arm) with 80% power. Table 1 provides

estimated differences that can be detected with this sample size for different CRC screening referral rates. Lost to follow-up either due to death or the Veteran leaving the VA system will be minimal as outcome data are collected administratively. We inflated the sample size to 500 patients to account for a 4% loss to follow-up. Patients who screen as eligible but who never log in to complete MeTree either on their own or in person will not provide data for the study and thus will not be counted toward the required sample size of 500. Thus, we may screen and consent >500 patients in order to enroll 500 who complete MeTree.

By design, patients may not be independent because they are clustered within a participating provider. The “relatedness” of patients within a PCP is measured by the intraclass correlation coefficient (ICC) and must be considered in the sample size estimation. We have a fixed number of PCPs (20 in each arm). The sample size for difference in proportions is adjusted by the intraclass correlation coefficient (ICC); we used an ICC of 0.02. Although an ICC is difficult to estimate in advance of a study, we believe this is an appropriate and conservative estimate based on our own and others’ research findings. A recent survey article reviewing outcomes from 31 studies found a median ICC of 0.01 (IQR 0 to 0.03). PASS 2008 was used for all sample size calculations.

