**The outcome for Aim 1 is rate of high-risk categorization.**

The analysis for this aim does not compare the outcome between arms as our aim is to determine if using MeTree to collect FHH improves the rate of high-risk identification for CRC compared to what is currently available administratively in VA. In our study design, both arms use MeTree to collect FHH, so the design for the aim is a pre-/post- comparison within Veterans. A binary variable will be created for each participant (1=presence of high-risk for CRC, 0=absence) at baseline (current practice) and following MeTree administration. We will test whether the rate of high-risk identification is higher following the MeTree administration compared to what is available in the medical record under current practice using a McNemar's test adjusted for PCP clustering. In addition to examining identification rates, specification of the source of identification of high-risk CRC will be important to formulating a standard identification strategy for clinical follow-up (e.g., referral to or receipt of colonoscopy screening).

**Table 2. Estimated differences in CRC screening/ surveillance uptake that can be detected between arms for different baseline screening/surveillance uptake with 80% power as well as different CRC screen referral rates**

Baseline referral rate for control arm	Sample size (control/ immediate )	Baseline screening/ surveillance uptake for control arm	Estimated difference between arms
60%	100/120	60%	18.0%
65%	100/120	65%	17.2%
70%	120/140	70%	15.0%

**The primary effectiveness outcome for Aim 2 is risk-appropriate CRC screening/surveillance referral for all patients, regardless of risk level.** Outcomes will be compared between arms to determine the impact of decision support on risk-appropriate referrals and screening/surveillance. The risk-appropriate screening/surveillance referral will be determined based on the MeTree algorithm. A binary variable will be created for each patient (1=adherent to risk-appropriate referral, 0=non-adherent to risk-appropriate referral) at 12-month follow up. The appropriateness of the referral will take into account if they were previously (prior to baseline visit) appropriately referred based on the current determination of their risk profile using the MeTree FHH data collection for both arms.

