## Protocol: The Impact of Family History and Decision Support on High-Risk Cancer Screening

defined by performance of any of them. For the referral for genetic consultation outcome, all patients eligible for genetic consultation based on their risk profile from FHH will have their EMR audited to determine whether a risk-appropriate genetic consult referral was documented. A binary variable will be created for each patient (1=presence of risk-appropriate genetic consult referral, 0=absence) at 12-month follow up. A similar variable will be created to indicate whether participants received the recommended genetic consultation. As these secondary outcomes are binary, we will follow the same modeling strategy using GEE as described for the primary outcome. In exploratory analyses, similar outcomes will be created for the other cancer types (breast and ovarian) as described for CRC. We will calculate descriptive statistics for these outcomes and, if sample size is adequate, we will fit similar GEE as described for CRC.

The primary analyses for this cluster-randomized trial will be conducted on an intent-to-treat basis; participants will be analyzed in the group to which they were randomized, regardless of intervention adherence. Additional supporting analyses focusing on alternative, more restrictive analytic cohorts (e.g., per-protocol analysis) may be considered as exploratory analyses to provide additional information about the impact of amount of exposure to the intervention. Given that the outcomes will be determined based on EMR review over a 12-month period, there should be very little missing data. The most likely scenarios are that a participant dies during the study or leaves the VA system before completion of the 12-month follow-up period. However, we do not expect this to occur at a high rate; as needed, we will explore the impact with sensitivity analyses.

The main conclusions drawn from this trial will be based on the pre-specified primary and secondary hypotheses outlined previously and will be tested with two-sided p-values at the standard 0.05 level. For both primary and secondary outcomes, stratification variables (provider type and patient age categorization) will be included in GEE models. Statistical analyses will be performed using SAS for Windows (Version 9.2: SAS Institute, Cary, NC) and R (<http://www.R-project.org>).

### Aim 3

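### Wait-list controls are approached about MeTree at months 10 and 11, and no rule keeps their decision support out of the 12-month referral window

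*Combined protocol and SAP*

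**What the plan says.** Several places put the control arm's exposure at 12 months. The PCP recruitment text (under the PCP inclusion criteria) gives enrollment or 12 months later as the two times for MeTree and decision support. The Immediate Condition paragraph says that the delayed group gets its choice of completion mode 12 months later. The Delayed (wait-list control) Condition paragraph says: "We will inform control participants that we will contact them 12 months post-consent to complete MeTree". It adds that study staff will contact neither control patients nor their PCPs during the 12 months.

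The same Delayed Condition text then sets earlier contacts. At month 10 after consent, controls are mailed a letter on how to complete MeTree. At month 11: "At 11 months following baseline, we will telephone control participants to assess preference for mode of completion using the aforementioned procedures". Controls not reached by month 12 get another letter and up to six more weeks of calls. On the note to the PCP: "We will follow the same procedures as in the immediate arm with regard to uploading the PCP decision support document requiring PCP signature". PCPs may order tests for controls found to be high-risk.

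Under Procedures (both groups), the delayed arm's exit survey on using MeTree is given in the same call as the self-reported screening survey, which is set at 12 months after consent.

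The primary effectiveness outcome for Aim 2 is defined under Analyses for Aims 1-2: "A binary variable will be created for each patient (1=adherent to risk-appropriate referral, 0=non-adherent to risk-appropriate referral) at 12-month follow up". The arms are compared by intent to treat.

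**The concern.** A wait-list comparison needs the control arm to stay untreated until its outcome has been read. Here the outreach that leads to MeTree starts one to two months before that date, and two safeguards are missing. No sentence gives an earliest date for a control's login or for the PCP note. No sentence closes the referral outcome when a control completes MeTree.

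Referral can follow quickly. It is found from procedure codes, orders, laboratory reports and notes, and a PCP can place an order after signing the note without seeing the patient. An order prompted in this way before month 12 would be scored as a control-arm success. The bias would run toward no difference, and the readiest responders among controls would be exposed first. A null result could then not be told apart from a diluted one.

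**Working it through.** **Timing, counted from consent**

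| Month | Control-arm event in the plan |
|---|---|
| 0–12 | No study contact with patients or PCPs |
| 10 | Letter on how to complete MeTree |
| 11 | Call about mode of completion |
| 12 | Stated time for MeTree; referral outcome read; screening call with the MeTree exit survey |
| 12 to about 13.5 | Further calls to controls not yet reached |

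The first row conflicts with the second and third. In the Immediate Condition text, the choice of mode leads to registration and release of login details. The access condition under Procedures (both groups) is HIPAA authorization or its waiver, not a date. If the 12-month call is on time, a control who can answer the exit survey in it has already used MeTree. Completion between months 11 and 12 is therefore possible and plausible.

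**The plan's own figure**

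Inputs, all from Analyses for Aims 1-2:
- Test: "Based on a type I error rate of 5% and Z test for the difference of two proportions adjusted for provider clustering", and the hypotheses "will be tested with two-sided p-values at the standard 0.05 level".
- Effect: control rate 60%, sized "to detect a 13% difference (i.e., 73% in the immediate arm) with 80% power". Table 1 gives the difference as 13.2 points.
- Size: 240 patients and 20 PCPs per arm, so 240/20 = 12 per PCP.
- ICC 0.02, so the design effect is 1 + (12 − 1) × 0.02 = 1.22.

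With 60% vs 73.2% and unpooled variance:
- n = (1.960 + 0.842)² × (0.60×0.40 + 0.732×0.268) / 0.132² = 196.5
- 196.5 × 1.22 = 239.7 per arm, which reproduces 240.

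With the rounded 13 points, power at 240 per arm is 78.8% (unpooled) or 78.2% (pooled). This is the undiluted baseline below.

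**Effect of dilution**

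Let f be the share of controls who complete MeTree before month 12, and g the share of the 13-point effect realised in them before the window closes. The documents give neither, so both are assumptions.
- Control rate: p_c = 0.60 + 0.13 × f × g. Immediate arm: p_t = 0.73.
- Effective n per arm: 240/1.22 = 196.7.
- Unpooled power: Φ(d/SE − 1.96), with d = p_t − p_c and SE = √{[p_c(1 − p_c) + p_t(1 − p_t)]/196.7}.

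Example, f = g = 25%: p_c = 0.6081, d = 0.1219, SE = √(0.4354/196.7) = 0.0470. Then d/SE = 2.59 and power = Φ(0.63) = 73.6%.

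| f | g | Rise in control rate (points) | Power, pooled / unpooled |
|---|---|---|---|
| 0 | – | 0 | 78.2% / 78.8% |
| 10% | 10% | 0.13 | 77.4% / 78.0% |
| 25% | 10% | 0.33 | 76.2% / 76.8% |
| 25% | 25% | 0.81 | 73.0% / 73.6% |
| 50% | 25% | 1.63 | 67.3% / 67.8% |
| 50% | 50% | 3.25 | 54.6% / 55.0% |

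**The case against.** The strongest reply is that the month-11 call is preparatory: staff learn the preferred mode, and completion follows at month 12, as the PCP recruitment text and the two condition paragraphs state. The call is described only as asking about mode, and nowhere is a login released or a note uploaded at month 11. Other features also slow early exposure:
- Access waits for HIPAA authorization unless it is waived.
- Patients have a worksheet for gathering history from relatives first.
- Calls run to six weeks past month 12, so some completions will come late.
- Controls may have no appointment near month 12, whereas the immediate arm is recruited around one.
- The sentence on PCPs ordering tests concerns high-risk controls, whereas the primary outcome covers every risk level.
- The joint exit survey also fits completion right at month 12.

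Most of this stands. A reader might infer from the month-11 call that the control arm is in fact treated from then on. The documents do not support that, because their explicit date for control MeTree is 12 months. The objection also shows that large values of f and g have no support in the text, so the near-zero cases belong in the range.

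It does not remove the point. The no-contact statement is contradicted by the contacts that follow it. A control who is reached at month 11 and has authorized access meets no stated hold, and the outcome has no cut-off at exposure.

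**Conclusion.** The plan contradicts itself on when controls are approached, and it lacks a rule keeping their decision support outside the 12-month referral window. Exposure inside the window is permitted and plausible, but it is not stated to occur. Any effect on the primary comparison is toward no difference.

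The size cannot be derived from the documents. Power falls by about one percentage point or less if the control rate rises 0.1 points, and by about 24 if it rises 3.25 points; if controls wait until month 12 there is no loss from this source. These figures rest on the plan's 60% vs 73%, 240 per arm and ICC 0.02, and on assumed f and g. The design has no spare power at the stated effect, so even modest dilution would count.

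Control-PCP education is a separate source of contamination. It is timed from the first participants' consent, so it can fall earlier in the windows of later-enrolled controls. The figures above do not include it.

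**What to change.** **Controls not yet contacted.** Reconcile the PCP recruitment text, the Immediate and Delayed Condition paragraphs and the 12-month survey text. State that the letter, the call, release of the login and upload of the PCP note all follow that patient's 12-month outcome date. The delayed arm's MeTree exit survey then has to leave the 12-month screening call. Cost: protocol wording, and control MeTree one to two months later.

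**Controls already contacted.** Record the dates of MeTree completion, note upload and referral. Identify control referrals dated after completion or note upload but before month 12, and report their number instead of taking them as usual care unchecked. Keep the 12-month intent-to-treat analysis as primary, and add a sensitivity analysis that ends the referral window at month 10 from consent in both arms, before the letter. Cost: date fields in the chart abstraction, a short SAP addition, and two months less follow-up in that analysis only. Making the month-10 window primary is not needed, since it would change the endpoint.

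Neither step removes the control-PCP education timed from the first participants' consent, which needs its own remedy.
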